#### **11E2.** Laboratory samples for Combination therapy pilot study

Subjects will have the following samples collected at baseline (pre- anakinra and - atorvastatin), 48 hours and 2 and up to 6 weeks (if still on study drug) (+/- 7 days) from enrollment:

**1. RNA collection:** Whole blood RNA will be collected using PAX gene tubes. RNA will be isolated according to the manufacturer's instructions and aliquoted and stored at -80°C.

2. Plasma and serum: EDTA plasma and serum will be collected for measures of inflammation.

#### 11F. Pharmacokinetic Samples (only collected in Phase I/IIa anakinra study)

- Dosing history (dates, times and amounts of doses)
- Height and weight on day of PK sampling
- Dates and times PK samples drawn
- PK samples around initial half of the 1st dose will be drawn during the following sample windows
  - 1. 1-3 hours after the dose
  - 2. 4-6 hours after the dose
  - 3. 7-9 hours after the dose, prior to administration of the second half of the dose at 12 hours
- Trough samples 48 hours, and 2 and 6 weeks after the start of the first dose

#### 11G. Echocardiography Core Lab for Phase I/IIa anakinra study and Combination therapy pilot study

An echocardiogram will be performed at the following time points:

- During initial hospitalization (as soon after admission as possible)
- 48 hours after enrollment in this study
- Study week 2 (Study day 14 ± 7 days)
- Study week 6 (Study day 42 ± 7 days)

2-D transthoracic echocardiograms (2-D Echo) will be performed on all KD subjects according to a strict pre-determined protocol at standard of care time points. All echocardiographic images will be analyzed by [name], Director of Non-Invasive Cardiovascular Imaging at Rady Children's Hospital San Diego. She will be blinded to patient data and clinical status. [name] will also assure adherence to the echo protocols across all echocardiogram technicians. 2-D Echo will be performed at KD diagnosis (within 24h of IVIG infusion) and again at two and six weeks following enrollment with sedation when clinically indicated. The internal lumen diameters of the left main (LMCA), proximal and distal LAD, circumflex, posterior descending, and proximal and distal RCA will each be measured. Dimensions of the LMCA, proximal LAD, and proximal RCA will be adjusted for body surface area and expressed in standard deviation units (Z-scores) (Manlhiot 2009). A variable "Z worst any vessel" will be created to capture the maximal Z score of the RCA or LAD at any time point, as well as the Z-score of the LMCA if an aneurysm is present there with a Z-score larger than that of the RCA or LAD. Coronary artery aneurysm will be defined as a Z-score of 2.5 or larger of the RCA or LAD(Nishiike 2006).

Additional echocardiographic data will be collected to assess aortic root dimensions and left ventricular dimensions and function, including indices of diastolic ventricular function (mitral inflow Doppler and tissue Doppler imaging), as recent reports have demonstrated abnormalities in each of these parameters following acute KD (Kato , Printz) Aortic root and ventricular dimensions and function will be expressed as body surface area (BSA)- or age-adjusted Z scores. A dilated aortic sinus diameter will be defined as a BSA-adjusted Z score  $\geq$  2.0 (Ravekes 2001). LV systolic dysfunction will be defined as an age-adjusted LV fractional shortening Z score < -2; LV diastolic dysfunction will be defined as an abnormal age-adjusted mitral inflow Doppler E'-wave, E'/A' ratio, or mitral deceleration time according to published normative data (Chaudhuri).

# 11H. Data Management for Phase I/IIa anakinra study and Combination therapy pilot study

Subjects will be assigned a unique study number. Demographic and clinical information including all numerical echo data parameters will be entered into an established, password-protected, database in use by our research group since 2001 (http://www-pediatrics.ucsd.edu/kawasaki) that currently contains data on over 1,200 KD subjects. The web portal uses the secure web application Research Electronic Data Capture (REDCap) (Harris 2009).

#### 11I. Patient adherence:

#### 1111. Patient adherence for Phase I/IIa anakinra study

Remaining syringes of anakinra will be counted at the 2 and  $\hat{6}$  week visits to assess patient adherence.

#### 1112. Patient adherence for Combination therapy pilot study

Remaining syringes of anakinra and tablets of atorvastatin will be counted at the 2 and 6 week visits to assess patient adherence.

# **12. Dosing Protocol**

#### 12A. Dose Levels

#### 12A1. Dosing for Phase I/IIa anakinra study

All subjects will be treated with IVIG (2g/kg) and aspirin (30-50 mg/kg/day divided every 6 hours; lowered to 3-5 mg/kg/day once sent home), which is the standard of care. In order to minimize the pain from subcutaneous injections, the first two doses of anakinra have been administered intravenously and divided every 12 hours for the dose escalation part of the study (i.e. 4 mg/kg/day is 2 mg/kg every 12 hours for two doses). As has been published in the peer-reviewed literature, we administered the dose by bolus over a 1 to 3 minute period (Opal 1997). As anakinra is formulated for intravenous administration, dilution is not necessary prior to administration. The unused material is discarded in a medical waste container after each administration. See **Appendix A** for details regarding preparation of the study drug for administration of less than 20 mg.

All subsequent doses are administered subcutaneously starting 24 hours after the first dose of the medication. This study has 3 dose levels (4 mg/kg/day, 6 mg/kg/day, and 8 mg/kg/day), with a maximum dosage of 200 mg daily (**Table 5**).

If the daily dose of anakinra for a subject is  $\leq$  100mg, then the subject will receive a subcutaneous injection of anakinra once daily. If the daily dose of anakinra is greater than 100 mg (with a max dose of 200 mg daily), then the dose will be split in half with administration subcutaneously every 12 hours (i.e. a total daily dose of 150 mg will be administered as 75 mg subcutaneously every 12 hours).

Table 5. Dose Levels					
Dose Cohort	Dose Level	Number of Subjects			
1	4 mg/kg/day	3-6			
2	6 mg/kg/day	3-6			
3	8 mg/kg/day	3-6			
ТОТ	AL	9-18			

Due to anakinra's predominant renal clearance, its dose is reduced in adults with significant renal dysfunction, 30mL/min (30% of normal adults). Given immaturity in renal function of infants, no infants will be enrolled during the first 4 weeks of life. At the age of 4 weeks, the typical GFR for a term infant is approximately 1.5 mL/min/kg (Rhodin et al. Pediatr Nephrol. 2009 Jan;24(1):67-76.). This represents 40-45% of the mature adult value (allometrically scaled), or approximately 50% above the threshold for dose reduction due to renal dysfunction in adults (45 mL/min/1.73m^2). We will require that individual study participant infants have renal function significantly better than eGFR of 30 mL/min/1.73m^2. At 4 weeks of age, the original infant Schwartz equation predicts a eGFR of 35 mL/min/1.73m^2 with a serum creatinine of 0.7 mg/dL. To provide an additional safety buffer and account for more specific creatinine assay in use today, we will only enroll infants with screening Scr  $\leq 0.50$  mg/dL, approximately equivalent to an eGFR of 45 mL/min/1.73m^2. For children  $\geq 1$  year of age who may be eligible for enrollment based on weight, higher Scr will be acceptable as long as the eGFR remains at least 45 mL/min/1.73m^2. Calculations will be made with the widely accepted modified Schwartz equation (http://www.globalrph.com/specialpop.htm). As we do not expect renal abnormalities to occur with KD or because of anakinra, Scr will only be assessed at baseline.

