## 11D. Data Collection

#### 11D1. Data collection for Phase I/lla anakinra study

#### 1. Demographic data:

- a. Patient's age at KD onset, sex, self-reported ethnicity of each biologic parent
- 2. Clinical data:
  - a. Physical findings confirming the KD case definition(Newburger 2004)
  - b. Illness day at study entry
  - c. Response to IVIG (IVIG-resistance will be defined as persistent or recrudescent fever (T≥38.0°C rectally) ≥36 h and < 7d following the end of the IVIG infusion (2g/kg) ([name] 2008).
  - d. Name, dose and indication of concomitant medications taken while on study
  - e. Complete white blood count (WBC), hsCRP, erythrocyte sedimentation (ESR), fibrinogen, and alpha-1-antitrypsin levels at baseline, 48 hours (not ESR as IVIG recently administered), 2 weeks and 6 weeks (if still on study drug) after drug administration
  - f. Serum creatinine at baseline prior to receiving study drug
  - g. Severity and duration of infections (with any associated cultures or diagnostic testing) during study
  - h. Echocardiographic data at baseline, 48 hours, and 2 and 6 weeks (standard of care for patients with CAA)

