#### 2. Clinical data:

- a. Physical findings confirming the KD case definition (Newburger 2004)
- b. Illness day at study entry
- c. Response to IVIG (IVIG-resistance will be defined as persistent or recrudescent fever (T≥38.0°C rectally) ≥36 h and < 7d following the end of the IVIG infusion (2g/kg) ([name] 2008).
- d. Name, dose and indication of concomitant medications taken while on study
- e. Serum creatinine at baseline prior to receiving study drug
- f. Severity and duration of infections (with any associated cultures or diagnostic testing) during study
- g. Complete blood count, CRP, hsCRP, ESR, aspartate aminotransferase (AST), and ALT at baseline, 48 hours (not ESR as IVIG recently administered), and 2 and 6 weeks
- h. CK and fasting lipid panel at baseline (after enrollment), 48 hours, and 2 and 6 weeks (if still on study drug)
- i. Echocardiographic data at baseline, 48 hours, and 2 and 6 weeks (standard of care for patients with CAA)

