#### 11E. Laboratory Samples

#### 11E1. Laboratory samples for Phase I/IIa anakinra study

Subjects will have the following samples collected at baseline (pre- anakinra), 48 hours and 2 and up to 6 weeks (if still on study drug) (+/- 7 days) from enrollment:

**1. RNA collection:** Whole blood RNA will be collected using PAX gene tubes. RNA will be isolated according to the manufacturer's instructions and aliquoted and stored at -80°C.

**2. Plasma, serum, and heparinized whole blood collection:** EDTA plasma and serum will be collected for measures of inflammation. Whole blood (5 ml in large green top) in a sodium heparin tube will be collected for T cell subset and cytokine studies.

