# 16. Pharmacokinetic Analysis for Phase I/IIa anakinra study

The area under the concentration-time curve (AUC) around the first dose for anakinra will be roughly estimated as the initial concentration (the concentration extrapolated back to time zero) divided by the elimination rate, if the elimination appears first-order (log scale) or zero-order (linear scale). We will also roughly estimate the AUC using the trapezoidal rule up to the last measurable concentration. The extrapolated area after the last concentration will be estimated as  $C_{last/\lambda z}$ , where  $C_{last}$  is the last measurable concentration and  $\lambda z$  is the terminal slope of the curve. AUC from time 0 to infinity AUC0-. S calculated as AUC0-last +  $C_{last/\lambda z}$ . Noncompartmental oral clearance rate (Cl/FNC) is calculated as the ratio of dose to AUC0-. Apparent volume of distribution (Vd/FNC) is calculated as Cl/FNC over  $\lambda z$ . Half-life ( $t_{1/2}$ ) is calculated as 0.693/ $\lambda z$ . Plasma anakinra trough concentrations collected in the subacute phase (weeks 2 and 6) will be compared to the 48 hour post-dose concentration collected during the acute phase (study day 2). AUC0-, Cl/F1-C (oral clearance from 1-compartment model), and Vd/F1-C (volume of distribution from 1-compartment model) will also be determined using a 1-compartment model. This second modeling approach will be used because the data are relatively sparse for an intensive PK study, which may limit our ability to estimate every parameter for some patients.

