# 18. Measures of Activity

#### 18A. Measures of inflammation for Phase I/IIa anakinra study

Transcript abundance will be measured in whole blood by microarray. Levels of hsCRP,  $\alpha$ -1antitrypsin and fibrinogen, and the WBC and ESR will be measured in the hospital clinical laboratory. Levels of TNFaR1 and R2, IFNg, IL-1 RAP, IL-1R1 and R2, MMP9, caspase-1, IL-6R, IL-18RAP, IL-12, sIL-2R, TGFb and IL-10 will be measured by ELISA. Results of transcript abundance and measures of inflammation will be compared to database controls from the KD Research Center (>600 KD patients with available RNA and plasma samples in our biorepository) matched (1 case: 2 controls) by age (± 2 yrs. with lower limit of 2 yrs.), sex, and coronary artery Z-score.

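### Phase I/IIa schedules creatinine only at baseline; adding it to blood draws already planned is a cheap improvement (optional in the pilot)

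*Combined protocol and SAP*

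**What the plan says.** Section 12A1 (Phase I/IIa) states the schedule and its reason: "As we do not expect renal abnormalities to occur with KD or because of anakinra, Scr will only be assessed at baseline". The data collection lists of both studies (11D1 and 11D2) carry the same item: "Serum creatinine at baseline prior to receiving study drug".

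Section 12A1 also explains why renal function matters for exposure. It refers to anakinra's "predominant renal clearance, its dose is reduced in adults with significant renal dysfunction", notes that infant renal function is immature, and sets entry at an eGFR of about 45, against an adult dose-reduction threshold of 30. Infants may enter from 28 days (11B1). Renal limits apply at entry only (11C1, 11C2).

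Blood is drawn after dosing in both studies. Phase I/IIa collects serum and plasma at "48 hours and 2 and up to 6 weeks (if still on study drug"), and section 18A has several markers "and the WBC and ESR will be measured in the hospital clinical laboratory". The pilot runs "aspartate aminotransferase (AST), and ALT at baseline, 48 hours" and later. In Phase I/IIa, section 11F records "Height and weight on day of PK sampling", and section 16 says: "Plasma anakinra trough concentrations collected in the subacute phase (weeks 2 and 6) will be compared to the 48 hour post-dose concentration".

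Safety is the primary outcome of both studies (7F1, 7F2). Sections 13A and 13B count an abnormal laboratory change as an adverse event, related or not, and list renal failure among the SAEs.

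**The concern.** The plan treats renal function as important enough to restrict entry, checks it once, and then doses for 2 or 6 weeks. If no renal laboratory event appears in the safety tables, part of the reason will be that no renal test was scheduled. The expectation in 12A1 may well be right, but the study cannot support it with data.

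In Phase I/IIa there is a second consequence. If a week 2 or week 6 trough differs from the 48-hour value, nobody can check whether renal function at that visit also differed. Height and weight are already recorded on PK days, so creatinine is the only missing input for an eGFR.

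In the pilot only the safety reason applies: children are at least 2 years old (11B2) and no PK samples are taken (11F).

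**Working it through.** **1. Schedule.** From 11D1, 11E1, 11D2 and 11E2:

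| Visit | Phase I/IIa blood work | Creatinine | Pilot blood work | Creatinine |
|---|---|---|---|---|
| Baseline | yes | yes | yes | yes |
| 48 h | yes | no | yes | no |
| Week 2 | yes | no | yes | no |
| Week 6 | if still on drug | no | AST and ALT; CK and lipids if still on drug | no |

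Scheduled on-treatment creatinine is therefore 0 of 2 visits, or 0 of 3 where week 6 blood is drawn. No other renal test is listed.

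**2. The plan's own margin.** 45/30 = 1.5, which reproduces the statement in 12A1 that the limit lies about 50% above the threshold. The fall needed to use up that margin is (45 − 30)/45 = 33%.

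**3. The margin in creatinine.** Section 12A1 names the modified Schwartz equation without writing it out. I assume the form eGFR = k × height / Scr, so eGFR × Scr is constant at fixed height. Starting from 0.50 mg/dL at eGFR 45, the product is 22.5. At eGFR 30, Scr = 22.5/30 = 0.75 mg/dL, a 1.5-fold rise.

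**4. A pair not to mix in.** Section 12A1 also gives 0.7 mg/dL at eGFR 35, from the original infant equation. Its product is 24.5, which puts eGFR 30 at 24.5/30 = 0.82 mg/dL. That is 0.82/0.50 = 1.63-fold, and the same pair gives eGFR 24.5/0.50 = 49 at the entry limit, so the fall to 30 would be 39%. It does not describe a 33% fall from 45, and 12A1 itself says the 0.50 limit allows for a newer assay.

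**5. Form of the flag.** The entry limits alone would miss large changes. An infant rising from 0.20 to 0.45 mg/dL (2.25-fold) stays below 0.50, and a child falling from eGFR 120 to 50 (2.4-fold) stays above 45. A criterion of 1.5 times own baseline catches both. In addition, 11C1 excludes infants at 0.50 or more while 12A1 enrols those at 0.50 or less. At exactly 0.50 the two disagree, so that figure cannot serve as an absolute flag until this is settled.

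**6. Possible size for exposure.** The documents give no renal fraction of clearance, so I assume f = 0.5 to 0.9. With average exposure proportional to 1/clearance, a one-third fall in GFR multiplies exposure by 1/(1 − f/3): 1.20 at f = 0.5 and 1.43 at f = 0.9, a rise of 20% to 43%.

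**7. Reach.** Section 12E puts 18 to 24 subjects at the MTD if the third level is reached, and 11B1 reports 2 enrolled at 8 mg/kg by August 2017. If 8 mg/kg is the MTD, at most 18 − 2 = 16 to 24 − 2 = 22 remain. Already treated: 6 to 12 at the two lower levels (Table 5) plus 2, or 8 to 14. Check: 22 + 8 = 30 and 16 + 14 = 30.

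**8. What those children could show.** With 1 − (1 − p)^n, the chance of seeing at least one case at an assumed rate of 5% is 56% for n = 16 and 68% for n = 22. With no case, the one-sided 95% upper bound 1 − 0.05^(1/n) is 17.1% or 12.7%. The data would be descriptive, but without them there is no bound at all.

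**9. Tests and blood.** Phase I/IIa: 16 × 2 = 32 to 22 × 3 = 66 tests. Pilot: 10 × 2 = 20 to 10 × 3 = 30. If each needs 0.5 to 1 mL (assumed) and cannot share a tube, the total is 2 × 0.5 = 1 mL to 3 × 1 = 3 mL per child. For a 2.5 kg infant that is 0.4 to 1.2 mL/kg over the study, against 5/2.5 = 2.0 mL/kg per visit for the existing heparin tube (11E1).

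**The case against.** The strongest reply is that this is a reasoned choice. Section 12A1 states why creatinine is not repeated, bars infants in their first four weeks and adds an entry buffer. Renal clearance means that the kidney affects the drug level; it does not mean that the drug harms the kidney. Section 8B reports at least 39 children under 2 years treated at 1 to 15 mg/kg with essentially mild local reactions, and section 1 reports no drug-related SAE. Overt renal failure would be captured as an SAE, and unscheduled testing is not barred. All of this stands. A reader might infer that the schedule is an error or hides a known renal risk; the documents support neither.

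The PK reason is also limited. During dose escalation the first two doses were intravenous, with subcutaneous dosing from 24 hours (12A1), and section 16 compares acute with subacute disease. Adherence and dose timing add further variation. A reader might infer that creatinine would explain a trough difference. It would only allow one candidate explanation to be checked.

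What the reply does not answer is that the reason in 12A1 concerns toxicity alone. It does not address the trough comparison, and it leaves an expectation about the primary outcome without a scheduled test.

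**Conclusion.** The point holds as a cheap improvement to a disclosed choice, mainly for Phase I/IIa, where the safety and PK reasons combine. The gap is confined to symptom-free change and to scheduled tests. Its size is 0 of 2 or 3 on-treatment visits, with a 33% fall in eGFR enough to take a child at the entry limit to the adult dose-reduction threshold.

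A reader might extend the point with equal force to the pilot. The documents do not support that: the children are older, eGFR below 45 is excluded and there is no PK comparison, so the addition there is optional.

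The added values would not show causation, because all children receive IVIG and aspirin and may receive infliximab (14b). No sample size, power, alpha, DLT definition or stopping rule changes. The conclusion rests on the schedule as written. The exposure and detection figures rest on assumed renal fractions and event rates, and the 16 to 22 remaining subjects are an upper range, since section 1 shows accrual continuing in September 2017.

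**What to change.** For subjects still to be enrolled:

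- Amend 12A1 and 11D1 (and, optionally, 11D2) so that serum creatinine with eGFR is run on the existing samples at 48 hours, week 2 and, where blood is drawn, week 6.
- In 19A, tabulate creatinine and eGFR by visit with change from baseline. In section 16, show them beside the 48-hour, week 2 and week 6 troughs.
- Flag for review any creatinine at least 1.5 times the child's own baseline and any eGFR below 30. Review is by the investigators and DSMB in Phase I/IIa (20A) and by the investigators in the pilot (20B). Add no stopping or dose rule.
- Settle whether an infant at exactly 0.50 mg/dL is eligible (11C1 against 12A1) before using that value as an absolute flag.

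For subjects already treated, state in 19A that renal laboratory safety was not assessed on treatment by schedule, unless stored serum has the volume, stability and consent for a later assay.

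The cost is at most 3 more assays per child and no extra visit: about 32 to 66 tests in Phase I/IIa and 20 to 30 if the pilot is included. The downsides are possibly 1 to 3 mL more blood per child (assumed) and some incidental values to follow up. At low baselines a 1.5-fold rise is small in absolute terms (0.20 to 0.30 mg/dL), so a flagged value should be repeated before it is interpreted.

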#### 12A2. Dosing for Combination therapy pilot study

All subjects will be treated with IVIG (2g/kg) and aspirin (30-50 mg/kg/day divided every 6 hours; lowered to 3-5 mg/kg/day once sent home), which is the standard of care. Anakinra will be administered once or twice daily subcutaneously at 8 mg/kg/day with a maximum dose of 200 mg/day. If the daily dose of anakinra for a subject is  $\leq$  100mg, then the subject will receive a subcutaneous injection of anakinra once daily. If the daily dose of anakinra is greater than 100 mg (with a max dose of 200 mg daily), then the dose will be split in half with administration subcutaneously every 12 hours (i.e. a total daily dose of 150 mg will be administered as 75 mg subcutaneously every 12 hours).

Atorvastatin will be administered orally once daily at 0.75 mg/kg/day with a maximum dose of 80 mg/day.

#### 12B. Duration of Study Drug

#### 12B1. Duration of study drug for Phase I/IIa anakinra study

All subjects will receive 2 weeks of therapy. Subjects with an echo at 2 weeks that shows either a LAD or RCA z-score  $\geq$  2.0 will receive an additional 4 weeks of therapy to complete a total course of 6 weeks. All subjects will remain on study for the full 6 weeks whether or not they are receiving anakinra.

#### 12B2. Duration of study drug for Combination therapy pilot study

All subjects will receive 2 weeks of therapy. Subjects with an echo at 2 weeks that shows either a LAD or RCA z-score  $\geq$  2.0 will receive an additional 4 weeks of therapy to complete a total course of 6 weeks. All subjects will remain on study for the full 6 weeks whether or not they are receiving anakinra and atorvastatin.

